## Methods and Procedures

This study will involve two sessions, completed approximately one week apart. The sessions will be identical except that one session will involve active neurostimulation and the other will involve sham stimulation. We will use a double-blind, cross-over procedure so that across participants the sham session will be equally likely to have occurred first or second and so that both participants and experimenters will be unaware of which session includes the active simulation.

After providing written informed consent, participants will complete two short self-report measures of paranoid thinking:

- 1) The Paranoia Scale (PS; Fenigstein & Venable, 1992) is a self-report measure designed to assess sub-clinical paranoid thought. Scores range from 20-100 with higher scores indicating higher levels of sub-clinical paranoia. 3 minutes.
- 2) The State Social Paranoia Scale (SSPS; Freeman et al., 2007). The SSPS is a psychometrically sound 20-item self-report measure assessing current levels of paranoid, positive, and neutral thinking about others. Participants read each statement and rate how much they agree on a scale from 1-5. 3 minutes

Participants will then begin the neurostimulation portion of the session, which will last for 20 minutes. The participant will be set up with the tDCS material that will start real or sham stimulation, and participants will be informed that they may read or otherwise entertain themselves during this portion of the study. The two electrodes of the tDCS will be placed over the left and right ventrolateral prefrontal cortex. For active stimulation the electrical current will be initially increased in a ramp-like fashion over several seconds (5 seconds) until reaching 1.5mA, and stimulation will be maintained for 20 minutes until it ramps down (5 seconds). For sham stimulation, the electrical current will be increased in a ramp-like fashion over several seconds (5 seconds) until reaching 1.5mA to mimic the sensation present during the first 5 seconds of real stimulation, and then stimulation will be stopped without the participant knowing. The total duration of the sham tDCS will be identical to the active condition in order to appropriately blind the procedure.

Following the neurostimulation portion, the participant will be asked to sit quietly for 30 minutes. After that time has elapsed, the participant will complete the following behavioral measures in a random order:

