- 7) The Rosenberg Self-Esteem Scale (RSES; Rosenberg, 1965) is a 10-item self-report measure used to assess level of self-esteem. Responses are made using a Likert scale from 1-4, and higher scores indicate higher levels of self-esteem. The RSES shows good internal consistency ( $\alpha=.92$ ) and convergent validity. 3 minutes.
- 8) Brief Core Schema Scales (BCSS; Fowler et al., 2006). The BCSS is a short self-report measure of positive and negative evaluations of the self and others. It has good psychometric properties and has more independence from mood state than other similar measures. 3 minutes.
- 9) The Depression Anxiety Stress Scales (DASS; Lovibond & Lovibond, 1995) is a 21-item self-report measure of the related negative emotion states of depression, anxiety, and tension/stress. 3 minutes
- 10) PS & SSPS - see descriptions above.

At the end of the session, we will ask participants to report which session they believed they just received. This will allow us to assess the success of our blinding procedure.

A repeated-measures ANOVAs will be used to compare indices of paranoia and related constructs between stimulation conditions.

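### The stated repeated-measures ANOVA drops anyone with only one session and names no session term; a mixed model on all completed sessions is a cheap, minor improvement

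*Combined protocol and SAP*

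**What the plan says.** The Combined protocol and SAP, Methods and Procedures, describes a double-blind crossover: "This study will involve two sessions, completed approximately one week apart". One session is active and the other sham. Order is balanced by design, so that "across participants the sham session will be equally likely to have occurred first or second". Active stimulation runs for 20 minutes. Sham ramps up over 5 seconds and is then stopped.

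Outcomes are collected within each session, after stimulation and a 30-minute wait: "After that time has elapsed, the participant will complete the following behavioral measures in a random order". A person who finishes session 1 has therefore already supplied a full set of outcomes for one condition. The Paranoia Scale (PS) and State Social Paranoia Scale (SSPS) are also completed before stimulation in each session.

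The analysis is given in a single closing sentence: "A repeated-measures ANOVAs will be used to compare indices of paranoia and related constructs between stimulation conditions". It names the condition comparison. It mentions no session (period) term and no treatment of participants who attend only once.

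**The concern.** With two conditions, a standard repeated-measures ANOVA tests the mean of D = active minus sham. D does not exist for someone with one session, so that person's completed scores go unused. Three things could follow.

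- **Lost data.** This costs some precision, but little.
- **Session shift.** Scores may change between visits for reasons unrelated to stimulation, such as practice or familiarity. With equal numbers in each order this cancels. If more people are lost from one order, part of the shift appears as a condition difference.
- **Selection.** Suppose people with worse active scores in session 1 are less likely to return, and this dependence is weaker after sham. Active-first completers are then selected for good active scores, and their later sham scores regress towards the mean. That looks like benefit. A session term does not correct it, because the distortion lies in who remains.

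At stake is the active-sham contrast on each index, which is the only comparison the plan states.

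**Working it through.** The plan has no sample size, dropout or power figure to reproduce. The following shows how large the effect could be.

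**Inputs**
- From the document: two sessions, balanced order, condition contrast by repeated-measures ANOVA.
- Assumed: outcome SD 1, higher scores worse, true effect 0, within-person correlation ρ = 0.5, 0.7 or 0.9.
- Assumed leaving rule: after active-first, a share h of those above +0.84 SD (the top 20%) do not return, and 5% of the rest. After sham-first, 5% do not return whatever their score. h is 75% (strong) or 30% (weak).

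**Loss**
- Strong: active-first 0.20×0.75 + 0.80×0.05 = 0.19; overall (0.19 + 0.05)/2 = 12%.
- Weak: active-first 0.20×0.30 + 0.80×0.05 = 0.10; overall (0.10 + 0.05)/2 = 7.5%.

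**Session shift alone.** For a session-2 shift s, D is displaced by -s in active-first and by +s in sham-first completers. The displacement of the pooled mean is s × (n_SF - n_AF)/(n_SF + n_AF), where n_AF and n_SF are the active-first and sham-first completers. With s = -0.3:
- Strong: -0.3 × (0.95 - 0.81)/1.76 = -0.024 SD.
- Weak: -0.3 × (0.95 - 0.90)/1.85 = -0.008 SD.

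A session term removes this part.

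**Selection alone (no shift).** The mean active score of active-first stayers is m = -(h - 0.05) × φ(0.84)/(1 - loss), with φ(0.84) = 0.280.
- Strong: m = -0.70×0.280/0.81 = -0.242.
- Weak: m = -0.25×0.280/0.90 = -0.078.

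The bias of D in that order is (1 - ρ)m. With a session term the two orders are averaged, giving (1 - ρ)m/2. Without one, the weight on active-first is 0.81/1.76 = 0.460 (strong) or 0.90/1.85 = 0.486 (weak).

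| Rule | ρ | No session term | With session term |
|---|---|---|---|
| Strong | 0.5 | -0.056 | -0.061 |
| Strong | 0.7 | -0.033 | -0.036 |
| Strong | 0.9 | -0.011 | -0.012 |
| Weak | 0.5 | -0.019 | -0.019 |
| Weak | 0.7 | -0.011 | -0.012 |
| Weak | 0.9 | -0.004 | -0.004 |

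Large simulations agree to within about 0.001 SD. A random-intercept model with condition and session, fitted to all sessions, had bias below 0.001 SD in every one of these settings, with or without the 0.3 SD shift.

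**Effect on the test (assumed N = 40, 4,000 simulated trials, strong rule).** At ρ = 0.5 the two-sided 5% error rate of the ANOVA was 6.2% with no shift and 7.2% with the shift, against 4.8% and 5.4% for the mixed model. At ρ = 0.7 it was 5.0% and 5.7%, against 4.7% and 5.4%, which is within Monte Carlo error (about 0.35 percentage points). The standard error at ρ = 0.5 is √(2×0.5/35.2) = 0.17, so the -0.056 bias is about one third of it.

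**Where the bias is zero.** If leaving is unrelated to the score, complete pairs with a session term are unbiased. If leaving follows the same score rule in both orders, the biases cancel when the true effect is 0. With a true effect of -0.3 SD, ρ = 0.7 and the worst 20% of first sessions leaving, +0.012 to +0.018 remained.

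**Where the mixed model is worse.** If leaving after active-first depends on an unobserved stable trait under the strong rule, complete pairs with a session term are unbiased. The mixed model is off by about 0.242 × √ρ × (1 - ρ)/2: +0.043, +0.030 and +0.011 at ρ = 0.5, 0.7 and 0.9. In a harsher case, with the top 20% on the trait all leaving, it reached +0.07.

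**Precision.** With 10% completely random loss, the empirical SD of the estimate was 0.166 for pairs and 0.165 for all sessions at ρ = 0.5, and 0.130 and 0.129 at ρ = 0.7.

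**The case against.** The strongest reply is that the selection bias needs a particular and rather strong pattern. Finding 20 minutes of current unpleasant is not the same as scoring worse on paranoia or attribution measures. If discomfort drives leaving and is unrelated to the outcome, selection bias is zero. The procedure is double-blind and the sham imitates the initial sensation, so it is not obvious that high scorers would leave after active but not after sham. When the contrast is 30% against 5%, the bias is 0.02 SD or less. The replacement model is not free of risk either: under trait-driven leaving its error is of similar size to the bias it would remove under score-driven leaving. Finally, PS and SSPS have pre-stimulation scores, which the calculation above does not use.

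All of this stands, and it limits the point. A reader might infer that active stimulation will drive out those who did badly, so that the ANOVA will manufacture a benefit. The documents do not support that: nothing in them links return to scores, and no dropout rate is given. A reader might also infer that the trial has no withdrawal or replacement rule. Not all of the text was available, so that cannot be claimed.

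The reply does not remove the session-shift leak. That needs only unequal loss by order and some change between visits, and the stated analysis has no term for it. Nor does it explain why one-session participants should be left to the default behaviour of the ANOVA.

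**Conclusion.** The point holds as a minor one. As stated, the ANOVA uses only participants with both sessions and names no session term. Unequal loss by order would let a session shift into the contrast, by about -0.008 to -0.024 SD for a 0.3 SD fall under the assumed losses. Score-dependent return that is stronger after active than after sham would add about -0.004 to -0.06 SD, and a session term alone would not remove that part. These sizes rest on assumed overall dropout of 7.5% to 12%, correlations of 0.5 to 0.9 and the leaving rules above. The available text gives no N, dropout rate or correlation, so the actual size cannot be fixed. For PS and SSPS the figures are only illustrative. With little dropout the issue is negligible, and the gain in precision alone would not justify a change.

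**What to change.** Replace the analysis sentence with wording such as:

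> Each index will be analysed with a linear mixed model (REML, Kenward-Roger degrees of freedom) with fixed effects for stimulation condition and session and a random participant intercept, using all completed sessions, including those of participants who complete only one. A complete-pairs analysis with a session term will be reported as a sensitivity analysis. The number not returning will be reported by order. Any material disagreement between the two analyses will be reported.

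State the assumption openly: the mixed model relies on return depending only on observed data, and the complete-pairs analysis is the safer of the two if return depends on a stable trait. For PS and SSPS, also say how the pre-stimulation scores enter the model.

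The cost is a change of wording and a few lines of code, with no extra participants, visits or procedures. With no missing sessions, the condition test is the same as that of an ANOVA with a session term.

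### PS and SSPS are scored before and after stimulation in both sessions, but the plan gives the pre-stimulation scores no role in the analysis, and the open readings differ widely in power

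*Combined protocol and SAP*

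**What the plan says.** All references are to the combined protocol and SAP, section Methods and Procedures.

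- **Design.** A two-session, order-balanced, double-blind cross-over of active against sham stimulation. "The sessions will be identical except that one session will involve active neurostimulation and the other will involve sham stimulation".
- **Before stimulation.** "participants will complete two short self-report measures of paranoid thinking", namely PS and SSPS; stimulation comes next. The SSPS is described as "assessing current levels of paranoid, positive, and neutral thinking about others".
- **After stimulation and a 30-minute rest.** Item 10 of the battery reads "PS & SSPS - see descriptions above". Items 1 to 9 are collected only at this point.
- **Analysis.** The closing sentence says that repeated-measures ANOVA will be used to "compare indices of paranoia and related constructs between stimulation conditions". It names no time factor, interaction, change score or covariate, and does not say that the pre-stimulation scores go unused.

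Taken together, each participant who completes both sessions has four PS and four SSPS scores, and the plan does not say how the four are combined. The supplied text gives no sample size, effect size, alpha or correlation.

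**The concern.** The analysis sentence fits three different tests of PS and SSPS.

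1. **Post scores only.** Valid, but differences in starting state between the two days remain in the error.
2. **Condition main effect over pre and post scores.** A score taken before stimulation cannot carry that session's stimulation effect, so averaging it in halves the effect.
3. **Condition-by-time interaction.** This is the test of change scores. It removes starting-state differences but adds the noise of the pre score.

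No single reading, fixed in advance, is biased or has an inflated type I error. Two things are at stake: precision on the two instruments that the protocol itself presents as measures of paranoid thinking, and the freedom to choose between tests of very different power once the data are visible.

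**Working it through.** The plan states no power or sample size, so there is no figure of its own to reproduce. The readings are compared on the within-person active-minus-sham difference.

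**Set-up.** D_pre and D_post are the active-minus-sham differences in pre and post scores. Both have variance 1 and their correlation is rho_d. D_pre has mean 0 and D_post has mean d.

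**Range for rho_d (assumed 0 to 0.7).** It is not the within-day correlation. With equal variances, within-session pre–post correlation rw and common between-session correlation rb, rho_d = (rw − rb)/(1 − rb). With assumed rw = 0.8:

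- rb = 0.8 gives 0/0.2 = 0
- rb = 0.7 gives 0.1/0.3 = 0.33
- rb = 0.5 gives 0.3/0.5 = 0.60

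So a high within-day correlation does not guarantee a high rho_d.

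**Large-sample variance relative to post-only, for the same effect d**

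| Analysis | Formula | rho_d 0 | 0.3 | 0.5 | 0.7 |
|---|---|---|---|---|---|
| Post-only | 1 | 1.00 | 1.00 | 1.00 | 1.00 |
| Change score / interaction | 2(1 − rho_d) | 2.00 | 1.40 | 1.00 | 0.60 |
| Main effect over pre and post | 2(1 + rho_d) | 2.00 | 2.60 | 3.00 | 3.40 |
| Baseline-adjusted | 1 − rho_d² | 1.00 | 0.91 | 0.75 | 0.51 |

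The main-effect row arises because the mean of pre and post has effect d/2 and variance (1 + rho_d)/2. Rescaling to effect d multiplies that variance by 4. These ratios are also the ratios of required sample size.

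**Finite-sample cost of the covariate.** The adjusted variance is multiplied by 1 + 1/(N − 4). At N = 24 this is 1.05, so adjustment breaks even with post-only at rho_d = √(1 − 1/1.05) = 0.22.

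**Simulated power (%).** Assumed N = 24, d = 0.6, two-sided 5%, balanced order, an order term in every model, 40,000 replicates per cell.

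| Analysis | rho_d 0 | 0.1 | 0.2 | 0.3 | 0.5 | 0.7 |
|---|---|---|---|---|---|---|
| Post-only | 80 | 80 | 80 | 80 | 80 | 80 |
| Change score / interaction | 51 | 55 | 60 | 66 | 80 | 95 |
| Main effect over pre and post | 51 | 47 | 44 | 41 | 37 | 33 |
| Baseline-adjusted | 78 | 79 | 80 | 82 | 88 | 97 |

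**Other sample sizes.** With d reset so that post-only has about 80% power, baseline-adjusted power at rho_d 0 / 0.3 / 0.5 / 0.7 is 76/80/87/96% at N = 16 (d = 0.75) and 79/83/89/97% at N = 40 (d = 0.455).

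**Error rates under no effect (N = 24).** Each method used alone rejects about 5% of the time. Counting a success when any of the three open readings is significant gives 11–12% per scale over rho_d 0 to 0.7. Choosing only between post-only and change score gives 8–9%.

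**The case against.** The strongest reply is that post-only is the natural reading. One sentence covers every instrument, and post-stimulation scores are the only data all of them share. On that view the main-effect reading, which produces the largest gap, is unlikely, and baseline adjustment is an alternative to the named ANOVA rather than one of its readings. This has weight, but the plan does not say post-only. Without the main-effect reading, post-only and change score tie at rho_d 0.5 but differ by 29 points at rho_d 0 (80 against 51%) and by 15 at 0.7 (80 against 95%).

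A second reply is that the gain from adjustment is uncertain. Below rho_d of about 0.2 it costs a little, and useful gains need about 0.5. The battery is given in random order, so the post PS and SSPS may follow different tasks on the two days, which could lower rho_d. PS may gain little if it behaves as a stable trait measure. All of this stands. It limits the expected benefit but does not supply the missing specification.

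Third, the pre-stimulation scores are introduced with "After providing written informed consent, participants will complete two short self-report measures of paranoid thinking", and consent is normally given once. If they were taken at session one only, the proposed covariate could not be built. The explicit statement that the sessions are identical points the other way, but the plan should confirm it.

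Finally, the SSPS covers paranoid, positive and neutral thinking, so naming the post-stimulation score does not by itself say which SSPS score is meant. That is fair and is taken into the fix.

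**Conclusion.** The point holds. The plan collects pre-stimulation PS and SSPS scores and gives them no role, so the test for these two scales is not determined. The variance ratios depend only on rho_d, given equal variances and no carry-over into the second session's pre score. The power percentages also rest on an assumed N and effect, since the documents give neither, and should be read as illustrations. Across the assumed range of rho_d, baseline adjustment beats or nearly ties every open reading. Its worst shortfall is at rho_d near 0: about 4 points against post-only at N = 16, 2 at N = 24 and 1 at N = 40. The 11–12% false-positive rate is a worst case for an open choice, not a claim about anyone's intent. The plan should be changed before unblinding, but no single reading is invalid, and only PS and SSPS are affected.

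**What to change.** For PS and SSPS, state before unblinding that:

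- the outcome is the post-stimulation score, naming which SSPS score is meant;
- conditions are compared with session (first or second) in the model, adjusting for that session's pre-stimulation score on the same scale as a within-person covariate, i.e. its deviation from the participant's mean pre-stimulation score;
- PS and SSPS are taken before stimulation in both sessions;
- the post-only comparison is reported as a sensitivity analysis, because the adjustment assumes that session-one stimulation no longer affects the session-two pre score about a week later.

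With two complete sessions, this equals regressing the active-minus-sham post difference on an intercept, a −1/+1 order term and the uncentred active-minus-sham pre difference. The intercept is the condition effect. The other instruments have no pre-stimulation measure and stay as post-only comparisons.

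The cost is wording and one degree of freedom per scale; no new data or visits are needed. If the sponsor prefers post-only or the interaction, naming that single contrast in advance still closes the open choice, though without the likely gain in precision.
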